#### Analysis principles and general considerations

Continuous data will be reported as means with standard deviation (SD) or confidence intervals (CI), or medians with interquartile range (IQR) and will be compared between groups using the unpaired t-test or Mann-Whitney U, depending on the distribution of the data. Equality of variances for TEA and PVB, respectively ICNB, will be assessed with Levene's test. Categorical data will be presented as counts and percentages and data will be compared using Mantel-Haenszel Chi-squared test. In case of zero cell counts and when pooling of categories is not opportune, the Fisher's exact test will be used (7,8). For all secondary outcome measures, the CI and/or p-values will be provided to express the level of statistical significance per outcome without additional correction for multiplicity (also p<0.027). An overview of the planned statistical tests per outcome measure for group comparisons can be found in the Supplemental material (Appendix A).

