#### Postoperative complications

Postoperative complications are registered until 30 days after surgery and categorized according to the Clavien-Dindo (CD) classification (13). They will be pooled and analysed as minor complications (CD 1 and 2), major complications (CD 3 and 4) and mortality (CD 5). Comparisons will be done with Mantel-Haenszel chi-squared test or Fisher's exact test (Table 3).

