#### Patient satisfaction

Patient satisfaction is scored from POD 0 until 3 in a patient diary using a 5-point Likert scale (extremely dissatisfied, dissatisfied, neutral, satisfied, extremely satisfied). This categorical outcome will be analysed as with Mantel-Haenszel chi-squared test or Fisher's exact test (Figure 4a).

Presence of chest tube

The presence of the postoperative chest tube will be registered in whole nights during hospital admission as outcome measure with differences between the groups analysed with T-test or Mann-Whitney U-test (Table 3).

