#### Degree of mobility

Degree of mobility was recorded in the patient diary using a 4-point Likert scale (only in bed, from bed to chair, from bed to the toilet, outside of the patient room). This categorical outcome will be analysed with Mantel-Haenszel chi-squared test or Fisher's exact test (Figure 4b).

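### For the two ordered outcomes, the sparse-table fallback to Fisher's exact test rests on an undefined pooling judgement and discards category order; a trend test kept throughout would avoid both

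*SAP*

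**What the plan says.** Under Analysis principles and general considerations, the SAP sets the default: "Categorical data will be presented as counts and percentages and data will be compared using Mantel-Haenszel Chi-squared test". It does not say whether this is the trend (linear-by-linear) form or the form stratified by centre. The fallback follows: "In case of zero cell counts and when pooling of categories is not opportune, the Fisher's exact test will be used". Two conditions must therefore both hold: an observed zero cell, and a judgement that categories should not be pooled. No criterion is given for that judgement. Both references attached to the rule concern 2×2 tables, going by their titles.

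Two secondary outcomes to which the rule applies are ordered scales:

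- Satisfaction: "Patient satisfaction is scored from POD 0 until 3 in a patient diary using a 5-point Likert scale". Its test: "This categorical outcome will be analysed as with Mantel-Haenszel chi-squared test or Fisher's exact test".
- Mobility: "Degree of mobility was recorded in the patient diary using a 4-point Likert scale". Its test: "This categorical outcome will be analysed with Mantel-Haenszel chi-squared test or Fisher's exact test".

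Appendix A lists the same pair of tests for both. Neither section, nor Appendix A, repeats the pooling condition, and no fallback that respects order is named. The caption of Figure 4 names generalized estimating equations for these same two outcomes.

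Secondary outcomes are tested at p<0.027 for TEA versus PVB and for TEA versus ICNB.

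**The concern.** The linear-by-linear test compares mean category scores on one degree of freedom. An empty end category simply contributes nothing to one arm's score, and the test remains usable. Fisher's exact test extended to a 2×K table (Fisher-Freeman-Halton) treats the levels as interchangeable. Moving from one to the other changes the alternative being tested, from a shift along the scale to any difference in distribution, and does so because of an observed count.

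Three things are at stake. Power falls for a consistent shift in satisfaction or mobility, which is the effect a superiority comparison looks for. The decision to pool or to switch is left open until the data of an unblinded trial are visible. And the two comparisons with TEA need not have the same zero pattern, so PVB and ICNB could be judged by tests that answer different questions.

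**Working it through.** **1. Group size.** The SAP gives 150 per arm and 12.6% drop-out: 150 × (1 − 0.126) = 131.1, so 131 per arm. As a check, the SAP's own non-inferiority inputs (SDs 19.57 and 23.33, difference 21.21 − 17.57 = 3.64, margin 17.5, one-sided 0.0135) give a standard error of √[(19.57² + 23.33²)/131] = 2.66 and power Φ[(17.5 − 3.64)/2.66 − 2.21] = 99.9%, consistent with the stated 99%. The SAP states no power for the categorical outcomes, so there is no figure of its own to reproduce there.

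**2. One table by hand.** Take a hypothetical 5-level table with 131 per arm, (0, 6, 20, 65, 40) against (2, 10, 28, 66, 25), scored 0 to 4.

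- Score sum in the first arm: T = 6 + 40 + 195 + 160 = 401. In the second: 10 + 56 + 198 + 100 = 364.
- Expected: E = (401 + 364)/2 = 382.5, so T − E = 18.5.
- Score variance over all 262: 2427/262 − (765/262)² = 0.738.
- V = 131 × 131 × 0.738/261 = 48.5.
- Chi-squared = 18.5²/48.5 = 7.05 on 1 df, **p = 0.008**.
- Exact linear-by-linear: p = 0.009. Fisher-Freeman-Halton: **p = 0.09**.
- With the two lowest levels pooled, (6, 20, 65, 40) against (12, 28, 66, 25), scored 0 to 3: T = 270, E = 252.5, V = 131 × 131 × 0.701/261 = 46.1, chi-squared = 17.5²/46.1 = 6.65, **p = 0.010**.

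At 0.027 the ordered test rejects with or without pooling; Fisher's test does not.

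**3. Power in tables with a zero cell.** 1,500 simulated trials per setting, 131 per arm, alpha 0.027, proportional-odds shift. The category distributions and odds ratios are assumptions, as the SAP gives none. LBL is the linear-by-linear Mantel-Haenszel test.

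| Scale, rare end level | Odds ratio | Tables with a zero cell | LBL | Exact LBL | Fisher | Loss, LBL to Fisher (points) |
|---|---|---|---|---|---|---|
| 5 levels, lowest 1% | 1.6 | 62% | 42.8% | 41.1% | 31.3% | 11.5 |
| 5 levels, lowest 1% | 1.9 | 67% | 71.1% | 67.9% | 57.4% | 13.7 |
| 5 levels, lowest 0.5% | 1.6 | 85% | 40.7% | 38.3% | 28.6% | 12.1 |
| 5 levels, lowest 0.5% | 1.9 | 89% | 67.6% | 64.8% | 55.3% | 12.3 |
| 4 levels, lowest 1% | 1.6 | 59% | 42.9% | 38.9% | 34.6% | 8.3 |
| 4 levels, lowest 1% | 1.9 | 62% | 72.4% | 69.4% | 62.7% | 9.7 |
| 4 levels, highest 1% | 1.6 | 38% | 47.1% | 44.4% | 38.6% | 8.5 |
| 4 levels, highest 1% | 1.9 | 34% | 76.6% | 74.4% | 68.0% | 8.6 |

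The exact ordered test loses only about 2 to 4 points, so most of the loss comes from ignoring order and not from exactness.

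**4. What pooling does.** 5 levels at 1/4/15/50/30%, log-odds shift 0.7 (odds ratio e^0.7 ≈ 2.0), 3,000 tables, with an unordered chi-squared test standing in for Fisher's. Power was 74.2% for the ordered test throughout, 62.1% if every zero cell led to the unordered test, and 73.8% if an empty lowest level was merged with its neighbour and the ordered test kept. With a 0.5% lowest level: 74.5%, 59.2% and 74.6%.

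**5. Different tests for the two comparisons.** With equal effects in both experimental arms, the zero-cell condition held for one comparison with TEA and not for the other in 9% to 37% of simulated trials (eight settings, end level 0.5% to 1%, log-odds shift 0.47 or 0.7 in either direction).

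**6. Type 1 error.** With no effect, rejection rates over all tables were 0.024 to 0.035 for every test and for the switch, against 0.027. The simulation error is √(0.027 × 0.973/1500) ≈ 0.004. There is no gross inflation.

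**The case against.** The strongest objection is that a reader might infer that one empty cell is enough to force Fisher's test. The SAP does not say that. Pooling stands in the way, and merging an empty lowest satisfaction level with its neighbour is the natural case for it. Step 4 shows that this restores the power. This stands, and it confines the loss to tables where pooling is declined. It does not remove the point, because nothing says when pooling is to be declined and the outcome sections and Appendix A omit the condition.

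Second, the loss presumes the trend form of Mantel-Haenszel, which the SAP never states. This also stands as a condition on the figures. If the centre-stratified form was meant, the fallback would instead drop the stratification factor.

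Third, the Figure 4 caption names generalized estimating equations for both scales, so the fallback might never be used. That conflict is real and unresolved; the outcome sections and Appendix A still specify the pair of tests.

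Fourth, a reader might extend the point to complications, which are given the same pair of tests. There the grades are grouped beforehand: "They will be pooled and analysed as minor complications (CD 1 and 2), major complications (CD 3 and 4) and mortality (CD 5"), and Table 3 lists the three groups as separate rows. In 2×2 rows category order plays no part, so the point does not reach them.

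Finally, these are secondary outcomes without further multiplicity control, and neither co-primary conclusion depends on them. That is correct and sets the weight of the point.

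**Conclusion.** The point holds as a minor improvement, not as an error that touches the trial's main conclusions. For satisfaction and mobility, the SAP's fallback replaces a test that uses order with one that does not, on a pooling judgement that is undefined and made after seeing the data. In tables that reach that branch the cost is about 8 to 14 points of power, and the PVB and ICNB comparisons may rest on different tests. Where the empty level is pooled there is practically no loss.

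The size depends on assumptions outside the SAP: the trend form of Mantel-Haenszel, an end level of 0.5% to 1%, proportional odds with odds ratios of 1.6 and 1.9, and 131 per arm. How often the Fisher branch would be taken cannot be derived. The 34% to 89% of tables with a zero cell is an upper limit under these assumptions, because pooling may intervene.

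**What to change.** In Analysis principles and general considerations, Patient satisfaction, Degree of mobility and Appendix A:

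- State that for ordered outcomes the Mantel-Haenszel test is the linear-by-linear form, with the scores given.
- Keep it for both comparisons with TEA whether or not cells are empty, with an exact or permutation p-value if the table is sparse. No pooling or switch decided on the data is then needed.
- Limit Fisher's exact test to 2×2 or unordered tables.
- Reconcile this with the generalized estimating equations in the Figure 4 caption, so that one method is named for each of the two outcomes.

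The cost is SAP wording only. No further data are needed. By the figures above, the exact version gives up about 2 to 4 points of power against the asymptotic ordered test.

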#### Protocol violation, adherence and deviation

Protocol violation is defined as non-adherence to the eligibility criteria, randomization process and study procedures, dictating that all patients should participate voluntarily and undergo an anatomical lung resection by VATS and one of the analgesic techniques (TEA, PVB or ICNB).

Protocol adherence defines that control patients should proceed to PVB catheter placement in case TEA catheter placement was unsuccessful; in case PVB too was unsuccessful, then ICNB should be done. Participants receiving TEA or PVB should have a provisional stop of the continuous analgesia at POD 2 and patients receiving TEA should have opioids administered through the epidural continuous mixture. Accidental luxation of the TEA or PVB catheter after surgery will not be seen as nonadherence.

Although the use of ERATS guidelines for enhanced postoperative recovery were advised by the protocol, it is expected that the level of implementation of each aspect of ERATS differs per hospital, for example the strict use of dexamethasone and 5-HT3 receptor antagonists. In addition, the availability of specific local anaesthetics (e.g. bupivacaine or ropivacaine) may vary and induce small between-hospital differences. To ensure equal distribution of small differences in ERATS aspects, we used treatment centre as stratification factor. Incomplete primary or secondary endpoints are considered a protocol deviation and are handled as missing data.

#### Intention-to-treat and per-protocol populations

Protocol violations such as not meeting the eligibility criteria, withdrawal from the randomization process, not performing an anatomical lung resection by VATS (conversion to thoracotomy, wedge resection or no resection), not utilizing TEA, PVB or ICNB as analgesic technique, or death on the day of the operation (resulting in unobtainable study results), will result in exclusion of the primary analysis. The ITT population will include all remaining randomized patients.

The PP population will include all patients from the ITT population who have adhered to the protocol. Patients will not be included in the PP population when the order of locoregional analgesic techniques in case of unsuccessful performance (TEA, PVB and then ICNB), the provisional stop at POD 2 in case of TEA of PVB, or when the addition of opioids to the epidural mixture were violated.

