#### **Trial population**

All screened patients assessed for eligibility and receiving the patient information folder will be recorded. The number of patients not randomized or excluded from the ITT and PP analysis will be

reported with reasons (e.g. withdrawal or lost to follow-up). Similarly, the number of randomized patients per analgesic group as well as the number of patients in the ITT and PP analysis will be reported. Progress of all participants through the trial is depicted in Figure 1.

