#### Baseline characteristics

Baseline characteristics will be described by trial arm as illustrated in Table 1 and assessed descriptively for the ITT group. In case of missing data, the denominator will not match with the total number of patients and this will be indicated in the corresponding table. Missing baseline characteristics will not be imputed.

Since stratification and randomization are applied to ensure a balanced distribution of baseline characteristics, we assume any differences to be caused by chance and to be a property of the sample, not of the population. Nevertheless, an imbalance of prognostic factors should not be ignored as it can influence the estimation of treatment effects. Therefore, all baseline characteristics in Table 1 will be compared between TEA versus PVB and TEA versus ICNB by using a validated method of standardized mean differences (SMDs) as described by Nguyen et al (9). The SMDs for these important prognostic variables will be reported in Table S1 (Supplemental material) and identified as potential imbalanced factors when the SMD exceeds 25%.

In Table 2, we will portray all details regarding the execution of the analgesic techniques including when it was performed (before, at the beginning, at the end or after the operation) and medication given (type, dosage and volume). For the TEA group we will report the test dose and continuous epidural mixture (local anaesthetics and opioids). The infusion rate (numerical in mL) from the time of placement until removal of the epidural catheter will be noted to calculate a total dosage (in milligram [mg] or microgram [ug]) of mixture given, reported as a continuous outcome. For the PVB group, the initial perioperative bolus given and the continuous infusion rate (in mL) until the day the PVB is stopped, will be recorded. For both TEA and PVB, also the number of days continuous infusion

was given will be noted. For the ICNB group the local anaesthetic given and the number of covered intercostal levels will be recorded. Any complication occurring during the execution of the analgesic technique will be reported in the text of the manuscript. Surgical and (general) anesthesia baseline characteristics will be shown in detail in Table 1.

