#### Analysis

For appointing non-inferiority, both the ITT and PP will be performed and both should attain to the predetermined non-inferiority margin (the one-sided 98.65% CI upper bound of the difference in proportions not exceeding 17.5%). For superiority (p<0.027), the ITT analysis will be considered as the primary analysis and the PP as a supportive analysis. For secondary outcome measures, solely the ITT analysis will be performed.

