#### Secondary outcomes

During hospital admission after surgery, all secondary outcomes will be measured from POD 0 until POD 3 and if applicable, until discharge from the hospital (e.g. duration of chest tube drainage). The follow-up outpatient clinic visit is at 2-4 weeks after surgery, according to local hospital protocols. Outcomes are collected up until 30 days after surgery, as described in the protocol. All secondary outcomes will be compared between TEA versus PVB and TEA versus ICNB in the ITT group and tested for statistical significance (p<0.027). The data will be presented as illustrated in Table 3.

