#### Harms

As described in the study protocol under "Adverse events and harms monitoring", the risk classification of the OPtriAL is scored as having negligible risk for study subjects. Moreover, there will be no new medicinal interventions, and all doses of applied anaesthetics are already used in daily practice. All adverse events per participant will be recorded until the end of the study and followed until they have abated, or until a stable situation has been reached.

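### The set called ITT is a modified ITT, and comparing complications and mortality only in it leaves out day-0 deaths and events in converted or otherwise excluded operated patients

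*SAP*

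**What the plan says.** In the SAP section on the intention-to-treat and per-protocol populations, several events count as protocol violations that take a patient out of the primary analysis. They are ineligibility, withdrawal, conversion, a wedge resection or no resection, and also "not utilizing TEA, PVB or ICNB as analgesic technique, or death on the day of the operation (resulting in unobtainable study results". The next sentence defines the analysis set: "The ITT population will include all remaining randomized patients".

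That set then governs everything beyond the co-primary outcomes:

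- Analysis: "For secondary outcome measures, solely the ITT analysis will be performed".
- Secondary outcomes: "All secondary outcomes will be compared between TEA versus PVB and TEA versus ICNB in the ITT group".
- Postoperative complications, registered to 30 days: "They will be pooled and analysed as minor complications (CD 1 and 2), major complications (CD 3 and 4) and mortality (CD 5". Table 3 has a row for each of these three categories, with a p-value for each block against TEA.

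Three other places touch on harms or exclusions:

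- Trial population promises the "number of patients not randomized or excluded from the ITT and PP analysis", with reasons.
- Baseline characteristics: "Any complication occurring during the execution of the analgesic technique will be reported in the text of the manuscript".
- Harms: "All adverse events per participant will be recorded until the end of the study".

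**The concern.** Several of the exclusions happen after randomisation: conversion, a lesser or no resection, use of none of the three techniques, and death on the day of surgery. A set defined by removing them is a modified ITT, whatever its label.

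For pain and QoR, leaving out a patient who died on day 0 can be explained, because there is nothing to measure. For mortality the explanation fails, because the death is itself the grade 5 event. Complications and later deaths in converted patients are likewise observable.

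At stake is the by-arm safety table. The SAP's background says that adverse events associated with TEA prompted interest in the alternatives, and it hopes for lower morbidity. A reader will take a table headed ITT to cover all randomised patients who were operated on. As planned, it would omit the most severe outcome when it occurs early, together with a group of patients selected by what happened in theatre.

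**Working it through.** **Tracing the rule**

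1. The population section removes the patients listed and defines ITT as the remainder. It speaks of exclusion from the primary analysis, but the same exclusion fixes the ITT set.
2. Analysis and Secondary outcomes confine all secondary outcomes to ITT.
3. Postoperative complications and Table 3 make grades 1 to 5 a secondary outcome.
4. Hence a day-0 death cannot be counted as grade 5, and no event in a converted or otherwise excluded operated patient is compared by arm.
5. Nothing else in the SAP fills the gap. Trial population gives counts and reasons. Baseline characteristics puts complications of performing the technique in the text. Harms covers recording and follow-up, with no analysis set and no by-arm summary. The checklist in Appendix B gives page references for item 20 (populations) and item 30 (harms), but only ITT and PP are defined.

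**Reproducing the SAP's own figure**

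Inputs from the SAP: 450 patients, 150 per arm, 12.6% allowance for conversions.

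- 131 / (1 − 0.126) = 149.9, about 150 per arm; 393 / (1 − 0.126) = 449.7, about 450. The allowance and the total agree.

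**Patients affected through conversion alone**

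- 450 × 0.126 = 56.7, about 57 in total; 56.7 / 3 = 18.9, about 19 per arm.
- Retained: 150 × 0.874 = 131.1, about 131 per arm.

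Other exclusions and day-0 deaths come on top.

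**Illustration for pooled complications** (event rates are assumptions; the SAP gives none)

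- Events left out per arm: with 30 to 70% of 19 converted patients having a complication, 19 × 0.3 = 5.7 to 19 × 0.7 = 13.3.
- Share of all patients with a complication, with 20 to 30% of the 131 retained patients having one: lowest 5.7 / (39.3 + 5.7) = 12.7%, highest 13.3 / (26.2 + 13.3) = 33.7%.
- Effect on the arm difference, with equal exclusion per arm: D(all) = 0.874 × D(retained) + 0.126 × D(excluded), so D(all) − D(retained) = 0.126 × [D(excluded) − D(retained)].

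| Assumed gap between the two differences (points) | Shift (points) |
|---|---|
| 10 | 1.26 |
| 20 | 2.52 |
| 30 | 3.78 |

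- Standard error of the planned difference, 100 × √(2p(1 − p)/131):

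| Assumed complication rate p | SE (points) |
|---|---|
| 0.2 | 4.94 |
| 0.3 | 5.66 |
| 0.4 | 6.05 |

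Every shift is below one standard error.

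**Illustration for mortality** (rates assumed)

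| Assumed mortality | Expected deaths per arm (131 × rate) | One death as share of expected |
|---|---|---|
| 0.5% | 0.66 | 153% |
| 1% | 1.31 | 76% |
| 2% | 2.62 | 38% |

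**The case against.** The strongest reply is about weight:

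- **No decision rule uses this table.** The trial's conclusion rests on pain and QoR, and complications are one of eleven secondary outcomes. That is true of the formal rule, but harms still inform any choice between the techniques.
- **The exclusions are open and planned.** Conversions are built into the sample size, and the flow of patients will show who was removed and why. This limits concealment, but a count of exclusions is not a by-arm comparison of deaths and complications.
- **The SAP refers to the protocol's harms section.** That section was not available here, and no claim is made about it. The point does not rest on missing safety detail: the SAP itself states which set is used for complications and mortality.
- **The numbers are mostly assumed.** The 12.6% is a 2017 national audit rate, and the trial excludes patients judged likely to be converted, so its own rate may be lower. The mortality percentages show how sparse deaths would be. They do not show how likely a day-0 death is, nor any bias. Both remarks stand.
- **Follow-up of excluded patients is not described.** The SAP does not say whether late-excluded patients have complications graded to day 30. This stands and limits what can be promised about cost.

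It could also be argued that conversion has nothing to do with the analgesic arm. The SAP does not show this. The trial is unblinded, and Table 2 has rows for preoperative placement of TEA, PVB at the start of surgery and ICNB at its end, so patients converted during surgery may have had different exposure by arm.

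**Conclusion.** The concern holds. Followed as written, the plan keeps a day-0 death out of the mortality comparison and drops complications and later deaths in converted and other excluded operated patients. This follows from the text and needs no assumption.

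The size is less certain. About 57 of 450 patients are affected through conversion if the SAP's 12.6% applies. Under the assumed rates the effect on pooled complications is modest. Deaths would be so few that a single omission could change the mortality row visibly, although that comparison will be imprecise either way. Neither the number of omitted events nor the direction of any bias can be derived from the SAP. It should be fixed before the final analysis. The co-primary sample size is not called into question.

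**What to change.** 1. **Complications and mortality.** Compare grades 1 to 5 by allocated arm in all randomised operated patients. Include day-0 deaths, conversions, wedge or no resection, patients who received none of the three techniques and those later found ineligible. Include patients who withdrew as far as their consent allows. State the set explicitly, since it still omits randomised patients who never reached surgery.
2. **Label and sensitivity analysis.** Call the present set modified ITT. Where outcome data exist, add a sensitivity analysis of both co-primary outcomes in all randomised operated patients as allocated. Leave the PP set as defined.
3. **Optional.** Report per arm how many patients received a fallback technique, with a supportive analysis of those who received their allocated technique, noting that this selects on successful placement.

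The cost is SAP wording and one or two extra tables. Item 1 can draw on the adverse events recorded per participant; whether these are complete and graded to day 30 in late-excluded patients needs checking. Item 2 is limited to whatever pain and QoR data those patients have. Item 1 is the essential change and can be made without the others.

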Non-inferiority for pain is obtained only if the upper limit of the 98.65% one-sided confidence interval (CI) of the differences of mean proportion of NRS  $\geq$ 4 between the PVB versus TEA and ICNB versus TEA remains below the predetermined absolute margin of 17.5% in the intention-to-treat (ITT) analysis as well as in the per-protocol (PP) analysis. This non-inferiority margin is based on data from a previous pilot study, in which the proportion of pain scores  $\geq$  4 in a group of patients receiving TEA was 17.57% (SD 19.57) and in patients receiving continuous locoregional analgesia 21.21% (SD 23.33). Since the baseline of 17.57% of moments of pain in the control group is low, we accept an absolute margin of 17.5% from a clinical point of view. This margin of non-inferiority, accepting more moments of pain in the intervention techniques as compared to the control group, is justifiable in combination with superiority regarding QoR. Superiority regarding QoR is defined as a significantly higher mean score during POD 1 and POD 2 (p < 0.027) in the ITT analysis. Taking the mean QoR score during POD 1 and POD 2 is a simplifying improvement of the original superiority definition in the published study protocol (1) without affecting the sample size calculation.

Secondary outcomes are: 1) pain scores during rest and mobilization at the recovery room, in the evening of the day of operation, and in the morning, afternoon and evening on POD 1 until POD 3, and at 2-3 weeks follow-up; 2) proportion of NRS scores ≥4 during mobilization during POD 0 until 2; 3) QoR-15 at POD 0, POD 3 and 2-3 weeks follow-up; 4) cumulative use of opioids and analgesics at POD 0 until 3 and the plain use of opioids at 2-3 weeks follow-up; 5) postoperative complications until POD 30; 6) hospitalisation; 7) patient satisfaction at POD 0 until 3; 8) time to removal of the chest tube; 9) time of an indwelling urinary catheter; 10) degree of mobility at POD 0 until 3 and 11) cost-effectiveness analysis (separate analysis).

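### Thirty-day complications and mortality are compared only in an ITT set that by rule excludes deaths on the day of operation, conversions and other removed patients

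*SAP*

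**What the plan says.** The SAP section on the intention-to-treat and per-protocol populations lists the violations that remove a randomised patient: not meeting the eligibility criteria, withdrawal from randomisation, an operation other than the planned thoracoscopic anatomical resection (conversion, wedge, or nothing resected), none of the three techniques used, "or death on the day of the operation (resulting in unobtainable study results), will result in exclusion of the primary analysis". The next sentence defines the population by what is left: "The ITT population will include all remaining randomized patients".

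The section headed Analysis states: "For secondary outcome measures, solely the ITT analysis will be performed". The opening of Secondary outcomes repeats the restriction: "All secondary outcomes will be compared between TEA versus PVB and TEA versus ICNB in the ITT group".

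The Summary of the study protocol lists among the secondary outcomes "5) postoperative complications until POD 30". The section Postoperative complications pools these by Clavien-Dindo grade into minor, major and fatal events, and Table 3 gives each group a row with a p-value for each technique against TEA.

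Three other sections bear on harms:
- Harms says "All adverse events per participant will be recorded until the end of the study" and followed up, but names no analysis set, summary or comparison.
- Trial population promises the number excluded from each analysis, with reasons.
- Baseline characteristics promises that complications during performance of a technique will be described in the manuscript text.

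**The concern.** The exclusions were written with pain and QoR in mind. A patient who dies on the day of operation has no QoR-15 score on days 1 and 2 and few or no NRS scores, so the stated reason makes sense there. It makes no sense for mortality, because the outcome is fully known.

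The other exclusions raise a similar problem. A patient converted to thoracotomy, or found ineligible afterwards, may already have received the allocated technique and can have a complication from it. Under the plan that complication enters no comparison.

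This matters because the SAP gives adverse events of TEA as the motive for studying alternatives, and names reduced morbidity as a hoped-for benefit. The complications table will be read as part of the case for or against changing practice.

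**Working it through.** **The plan's own figures first.** Inputs: 150 per arm, 450 in total, 12.6% drop-out for conversion, one-sided alpha 0.0135 and 99% power for pain (Summary of the study protocol); pilot values 17.57% (SD 19.57) and 21.21% (SD 23.33); margin 17.5 points.

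- Retained per arm: 150 × (1 − 0.126) = 131.1. Conversely, 131 / (1 − 0.126) = 149.9, so 150 per arm agrees with about 131 analysed.
- Pooled SD: √((19.57² + 23.33²)/2) = 21.53. Standard error: 21.53 × √(2/131) = 2.66. Expected difference: 21.21 − 17.57 = 3.64.
- Power: Φ((17.5 − 3.64)/2.66 − 2.21) = Φ(3.00) = 99.9%, consistent with the stated 99%.

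The sample size already allows for the loss of converted patients, so nothing in it is wrong on this point. The issue is which patients the harms outcomes are counted in.

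**Tracing the analysis set.**
1. Day-of-operation deaths, conversions, wedge or no resections, ineligible patients and those without a study technique are removed; the remainder is called ITT.
2. Secondary outcomes are analysed only in ITT (Analysis; Secondary outcomes).
3. Complications to day 30, with mortality as CD 5, are a secondary outcome.
4. Hence a day-of-operation death cannot appear in the CD 5 row, and no event in a removed patient appears in any between-arm comparison.
5. Later deaths and complications among retained patients are still compared.

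**Number of patients.** Conversions alone: 0.126 × 450 = 56.7, about 57 patients; 0.126 × 150 = 18.9, about 19 per arm. The SAP gives no rates for the other exclusions, which would add to this.

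**Share of complications lost.** The SAP gives no complication rates. Assume converted patients have r times the complication rate of the others, and let d = 0.126. The share removed is d·r / (d·r + 1 − d):

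| r (assumed) | Calculation | Share removed |
|---|---|---|
| 1 | 0.126 / 1.000 | 12.6% |
| 2 | 0.252 / 1.126 | 22.4% |
| 3 | 0.378 / 1.252 | 30.2% |

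**The case against.** **The exclusion may concern only the primary analysis.** The sentence does say so. However, the next sentence builds the ITT population from the same exclusions, and two later sections tie every secondary outcome to that population. The narrower reading is not available as the text stands.

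**The events are not hidden.** This is partly right. Day-of-operation death is a named exclusion reason and should therefore appear in the participant flow, and procedural complications are to be described in the text with no stated limit to ITT. A reader might infer that these deaths and harms vanish from the report altogether, or that harms of exposed patients are never compared. The SAP supports neither: about 131 patients per arm remain and are compared. What is missing is a between-arm comparison that includes the removed patients.

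**The protocol may settle it.** The Harms section refers to the protocol's section on adverse events, which is not at hand and may define a safety population. The absence of such a definition is therefore not the point. The point is that the SAP restricts secondary outcomes to ITT without exception, and complications are one of them.

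**The bias is unproven.** This stands. A reader might infer that the comparison is pulled towards no difference. The exclusions apply to all three arms, and the SAP gives no conversion or complication rates by arm, so no direction follows. The Table 2 shells suggest that TEA and PVB may often precede a conversion and ICNB may not, but they are counts to be filled in and do not fix the timing.

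**The size is uncertain.** This also stands. The 12.6% comes from a 2017 national audit, while the trial excludes patients with a high probability of conversion, so 57 may be too high.

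**Conclusion.** The point holds. Following the SAP literally gives a mortality row that cannot contain a death on the day of operation, and a complications comparison that leaves out about 57 of 450 patients on the plan's own conversion assumption, plus the other excluded groups. The comparison is incomplete and possibly biased, in a direction the SAP does not allow one to determine.

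Only the patient count follows from the SAP. The 12.6%, 22% and 30% shares of lost complications rest on assumed rate ratios of 1, 2 and 3.

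Severity: should be fixed. A rule that deletes deaths from a mortality outcome might suggest something graver, but complications are one of eleven secondary outcomes, and neither the co-primary conclusions nor the sample size depend on them.

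**What to change.** Add to the population section, to Analysis and to the opening of Secondary outcomes that postoperative complications and mortality are analysed by randomised arm in all randomised patients in whom anaesthesia or a study technique was started, regardless of conversion, eligibility or death on the day of operation. Use this set for the complication and mortality rows of Table 3. State that the exclusion for death on the day of operation applies only to the pain and QoR outcomes. A further listing by technique attempted is optional.

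The cost is SAP wording and one more analysis set. Complication rates will then include conversion-related events, which the report should say. The SAP states that adverse events are recorded for each participant, but it also treats conversions as late exclusions and does not say that their 30-day Clavien-Dindo follow-up continues. Completeness of that follow-up must be confirmed before the set is used.
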